5.2 Recruitment Methods

- For the pilot, we will purposefully sample 10 Veterans from each site (total of 20) and will aim to include 4 women Veterans (2 per site).
- For the main RCT, We will recruit 600 African-American Veterans with HTN. Veterans will be recruited from two geographically distinct VAMCs (Chicago and Philadelphia, Table 7) with a high proportion of African-American patients and known disparities in HTN control.
 - Jesse Brown VAMC in Chicago is a 189-bed hospital and teaching affiliate of the University of Illinois-Chicago and Northwestern University. The Jesse Brown VAMC and its four affiliated community-based outpatient clinics (CBOCs) in Chicago, Southern Cook County, and northwest Indiana provide primary care to roughly 30,000 veterans and 80% are African-American. Among primary care patients, approximately 18,000 have HTN.
 - Corporal Michael J Crescenz (CMJC) VAMC in Philadelphia serves over 90,000 Veterans, operating CBOCs in Fort Dix, NJ, Gloucester County, NJ, Horsham, PA, and Center City Philadelphia.
- Using VISTA data, we will review data for potentially eligible patients for up to 2 years preceding recruitment. We will identify patients with a listed diagnosis of HTN (ICD10 diagnosis codes: *I10, I11.0, I11.9, I12.0, I12.9, I13.0, I13.10, I13.11, I13.2, I15.0, I15.1, I15.2, I15.8 I15.9, I16.0, I16.1, I16.9, N26.2*) (further details on inclusion criteria listed below). The final generated list of potential participants will be kept in a computer file that is password protected and only accessible by the RA and project staff. Any printed list used by the RA in the clinic will be stored in a locked file cabinet when not in use. Staff will make all attempts to print the recruitment letters and labels, and stuffing the envelopes at the VA location, however if a location other than the VA is necessary for this task, all security requirements will be in place for transporting any study materials to the secondary work location of the RA's home; ie. a signed Authorization to Transport, and RA will use a locked safe to store printed materials containing PII. We will include both women and men in the study.
- Each potentially eligible Veteran will be sent a letter inviting participation, with an opt-out card. If no opt-out card is received in a two-week period, the RA will contact the Veteran by telephone, explain the study and ask several eligibility screening questions including the patient's race/ethnicity and access to a cell phone with texting capability. Competency will be assessed during the phone screen questionnaire which includes cognitive functioning questions.
- If the Veteran is eligible and wishes to participate, the RA will schedule a time for the Veteran to hold the visit over-the-phone.
- At the start of the over-the-phone study visit and at the start of the follow-up phone visit (for both pilot and RCT) the RA will confirm the Veteran's identity and confirm the address at which he or she will be located for the duration of the phone call. This will provide RAs the ability to notify emergency personnel in the event that an emergency response is needed for any reason.
- Intervention and control Veteran participants will both receive the same incentives. Each participant will receive a \$30.00 incentive per phone visit, for a total of two visits (in-person baseline visit and follow-up data collection visit). Payment method may vary by site and will be based on what is available and most convenient for the Veterans.

Participant may incur costs related to receiving or sending texts if they do not have an unlimited texting plan; they will be notified of this in our consent form.

Potential risk to participants when receiving/responding to texts while walking/driving etc.

- During enrollment of participants, RA's will review texting safety measures including avoidance of texting and driving (we will review available 'do not disturb' phone features with Veteran as desired), avoidance of texting while walking (or doing other mobile activity that requires visual attention); ensuring physical safety before pausing to review or respond to texts.

5.3 Informed Consent Procedures

- We will be obtaining a waiver of informed consent documentation for all study activities. We will be requesting a HIPAA Waiver to obtain the participant list from which to recruit. For over-the-phone visits we are submitting a waiver of documentation of informed consent.
- We will train site RA's at both sites in procedures to follow for baseline and follow-up visits. Screening for eligibility and competency will be conducted during the phone screen questionnaire which includes cognitive functioning questions. If the participant is eligible, able to complete the competency questions and is willing to participate, a baseline visit will be scheduled over-the-phone.
- The Bedford project manager will hold weekly training sessions including using Teams when needed to review and train RA's at local sites in obtaining informed consent and conducting visits.

5.4 Inclusion/Exclusion Criteria

- We will include Veterans who have been receiving care at the recruiting VA site for ≥ 1 year prior to recruitment, with 2 or more visits documented over the past year. We will include Veterans who have documented HTN (ICD10 diagnosis codes: *I10, I11.0, I11.9, I12.0, I12.9, I13.0, I13.10, I13.11, I13.2, I15.0, I15.1, I15.2, I15.8 I15.9, I16.0, I16.1 I16.9, N26.2*) during this 1-year period. We will include only patients who self-identify as African American or Black. In addition, participants must be on at least one medication for BP. Eligible participants will need to have access to their own or a family member's cell phone or smart phone for participation and they must be willing to use this phone for receipt of text messages over a 6-month period. Eligible participants will also need to have access to internet and a reliable device in order to watch videos. If Veterans do not have a BP monitor at home, we will arrange to have one sent to their home – they must be willing to take their own BP or have someone assist them in doing so. We will exclude Veterans who participated in our previous VA Stories study.

In addition, any Veteran who fails the memory and concentration questions asked in the screening survey will be excluded. Because hypertension management guidelines for pregnant females differ, pregnant women will be excluded; we have included this in the screening survey.

5.5 Study Evaluations

- We will pilot the process of (1) guiding the Veteran in at-home BP check; (2) selection of a preferred veteran storyteller after viewing all stories; (3) using this choice to inform selection of a texting protocol; (4) Receipt of 1 month of texts; and 5) follow-up assessment at the end of 1 month. Research assistants will collect field notes on items (1) (2) and (3). For item (4) we will collect data on implementation/process measures throughout the 4-week period (see Table 8 below, item 7 for details of these measures). We will also assess feasibility of two options for Veterans to access texts: (a) via regular texting, available on all text-enabled phones; (b) via HealtheDialog 'App' which allows study team tracking of text opening (but is available only on Smart phones).
- All data will be stored in accordance with VA policy.
- Only the study team and the PI will have access to this information.

For the randomized controlled trial, as listed in the table below, we will collect 7 data elements: (1) Veteran characteristics; (2) Intervention dose/exposure; (3) Narrative Communication measures; (4) Social Cognitive-Theory-based measures; (5) Hypertension management behaviors; (6) Blood Pressure (BP) (blood pressure will be checked by participant through home BP monitor at baseline and at 6 month follow up); and (7) Implementation Data including Process Measures and measures of Fidelity. We will gather these elements through initial data collection (CDW), over-the-phone screening survey, baseline visit and follow-up visit observations and surveys, texting system and phone calls to participant.

5.6 Data Analysis

• Table 8. Seven Key Data Elements		Timing	Source
1. Veteran Characteristics			
Participant Demographics	1	S,C	
Comorbidities, VA Utilization	1	C	
2. Intervention Dose/Exposure			
Number of videos watched and time spent viewing	2	S	
Which was selected video?	2	S	
3. Narrative Communication			
Video Transportation Scale	2	S	
Homophily (personal relevance)	2	S	
4. Social Cognitive Theory			
Beliefs About Medications (BMQ)	1,4	S	
Self-efficacy for hypertension (e.g.: MASES-R, PEPP)	1,4	S	
5. HTN management behaviors			
Avoid Salt, Be Physically Active, Monitor your BP (H-SCALE, PEMH)	1,4	S	
Talk with your doctor (H-SCALE)	1,4	S	
Take Your Medicines: Morisky ; and administrative data adherence (MPR)	1,3,4	S, C	
6. Primary Outcome (H1)			
Measured BP (systolic/diastolic)	1,4	BP, C	
7. Implementation Data/Process Measures/Fidelity			
Text message opening (subgroup)	3	T	
Responses to text assessment	3	T	
Confirmation of text receipt	4	S	
Phone calls for texting assistance	3	RA	
Staff time spent for implementation	3	RA	
Persistence/Early Discontinuation of Texting Protocol	3	T	
Reasons for discontinuation	5	P	

1=Baseline, 2=Immediately post-Video Viewing; P, 3=Repeated throughout 6-month study period, 4 = six-month follow-up; 5= phone call to drop-out

Source: S = Survey; C = CDW data; RA=Research assistant; T=Texting System;

P=phone call to participant; BP = Blood pressure cuff, standard protocol (For BP measurement at 6-months, we will pull CDW data for the entire study participation period)

With our recruited sample of 600 (and assuming follow-up rates, over-time within-person correlation, and BP standard deviations from our prior work (85% follow-up, correlation = 0.5, SD = 18 (equivalent to variance of 324)), we have over 80% power (alpha 0.05) to detect a difference of 5mm Hg. In fact, we calculated power for a range of scenarios, and are able to maintain the 5mm Hg detection with a lower follow-up rate of 82%.

Power for H2 & H3: Conceptually, the CTC intervention impact on blood pressure is possible because the intervention will have an effect on more proximal cognitive and behavioral outcomes (H2) that then mediate the main effect (H3). Thus, theoretically, power for group-by-time differences in the scales for H2 will be greater than H1, and thus we should be over-powered for these measures. We calculated H2 power for difference-in-differences analyses. As each of the scales were different, we report minimum detectable differences as effect sizes.

[name] will lead the data analysis in years 3 & 4, working closely with Drs. [name] and [name] (statistician, cost analyst) and programmer.

5.7 Withdrawal of Subjects

- If at any time the local site PI feels the study is inappropriate for a participant or due to medical reasons, the PI reserves the right to discontinue/withdrawal the subject from the study.
- If at any time a participant chooses to discontinue participation, they may do so with no repercussion to their care or future opportunities in research or other at the VA.

6.0 Reporting

- Because this is a low-risk trial of an educational DVD, we do not expect SAE's or AE's. We will plan to report any SAE's defined as death of participant or hospitalization, with data collected at 6-month follow-up. We will report SAEs identified in this manner within 5 business days of their identification. RA at site will notify the Local Site PI of any SAE and notify the Bedford project manager, who will then submit a Form 119 Unanticipated SAE to the appropriate SharePoint folder designated for Reportable AE/SAE.
- At the time of baseline visit, patients experiencing hypertensive urgency, as defined by JNC as Blood Pressure Systolic \geq 180 OR Diastolic \geq 120, regardless of symptoms, will be referred to urgent care and a notification letter will be sent to their primary care physician. All AE's reported at baseline and 6-month follow-up will be recorded by the RA and submitted to the Bedford Project manager, who will track and submit at Continuing Review.

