Missingness not at random may introduce bias. Advance planning through sound data collection and quality control will be used to minimize this bias. We will use all available data regardless of whether a patient has a complete record. Group means will be reported as least-squares means, the predicted marginal mean values, or those that would be expected with a balanced design. Participants with missing data will be compared to those without. Inverse probability weight in and pattern-mixture modeling using the longitudinal data structure, for non-ignorable missing data, will be considered.

Covariates for Adjustment Models

We will look at the balance of randomization and adjust for demographics and behavioral variables if imbalanced.

Data Transformations

N/A

Analytical Sets

We intend to include all patients in intent to treat analysis.

Monitoring Adverse and Serious Events

Because this is a low-risk trial of an educational DVD, we do not expect SAE's or AE's. We will plan to report any SAE's defined as death of participant or hospitalizations reported at 6-month follow-up.

At the time of recruitment, patients experiencing hypertensive urgency, as defined by JNC as Blood Pressure Systolic \geq 180 OR Diastolic \geq 120, regardless of symptoms, will be referred to urgent care and a notification letter will be sent to their primary care physician. If a patient reports symptoms related to the hypertensive urgency, even if before viewing the intervention DVDs, this will also be reported as an AE. AE's also include stress related to watching the DVD. All AE's reported at baseline and 6-month follow-up will be recorded and submitted at Continuing Review.

Analysis Plan

We will first identify key distributional features for all variables of interest (non-normality, skewness, ceiling or floor effects, presence of implausible values, outliers, etc.) and calculate descriptive statistics. We will document recruitment and retention with a CONSORT diagram. Following best practice, baseline differences between intervention and comparison groups will be based on standardized differences, not simply tests of statistical significance. All primary hypotheses will be tested by intent-to-treat; secondary analyses will account for important covariate imbalances between groups, levels of adherence to the intervention protocol, and missing data. All analyses will be two-sided, with alpha error = 0.05.

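### The 6-month follow-up is the only stated point for finding deaths and hospitalisations, with no procedure for participants who die or are not reached

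*Protocol*

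**What the plan says.** Protocol 6.0 Reporting defines SAEs by two event types and gives one time of collection: "We will plan to report any SAE's defined as death of participant or hospitalization, with data collected at 6-month follow-up". The SAP, under Monitoring Adverse and Serious Events, has: "We will plan to report any SAE's defined as death of participant or hospitalizations reported at 6-month follow-up".

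Other relevant text:

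- **Non-serious events** (Protocol 6.0): "All AE's reported at baseline and 6-month follow-up will be recorded by the RA".
- **Reporting clock** (Protocol 6.0): "We will report SAEs identified in this manner within 5 business days of their identification".
- **Visits** (Protocol 5.2): the incentive is paid "for a total of two visits (in-person baseline visit and follow-up data collection visit"). No visit is described between the two.
- **CDW** (Protocol 5.6, Table 8): the row "Comorbidities, VA Utilization" is sourced from CDW at baseline only. Refill adherence draws on CDW through the study. A note on the 6-month blood pressure adds that "we will pull CDW data for the entire study participation period".
- **Drop-outs** (Table 8): a phone call is planned, and the only item listed for it is the reason for discontinuation.

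Neither document links CDW, next of kin or any record check to deaths or hospitalisations for SAE reporting.

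**The concern.** One of the two SAE types is death, and a participant who has died cannot report at follow-up. Hospital admission also makes a missed follow-up more likely. The single stated collection point is therefore weakest for the events it is meant to find.

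Three things are at stake:

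- **Completeness.** SAE counts may be too low. If loss to follow-up differs by arm, so may the shortfall.
- **Timeliness.** The clock starts at identification, so an event soon after randomisation can surface about 6 months later with the plan fully complied with. Protocol 8.0 foresees DSMB reports, and these can contain only events already identified.
- **Interpretation of missing outcomes.** The SAP, under Missing Data/Subject Dropouts, will compare participants with and without missing data and will consider models for non-ignorable missingness. Without systematic capture of deaths, a blood pressure missing because of death cannot be told apart from ordinary loss.

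**Working it through.** **Inputs.** Sample size 600 (Protocol 5.1). Follow-up 85% with a lower scenario of 82%, within-person correlation 0.5, SD 18 mm Hg, difference 5 mm Hg, two-sided alpha 0.05 (SAP, Power Calculations; Protocol 5.6). No allocation ratio is stated, so 1:1 (300 per arm) is assumed. Neither document gives a death or hospitalisation rate.

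**Step 1: the plan's own figure.** The follow-up rate is used only in the power statement, which claims over 80%.

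- SD of change = 18 × √(2 × (1 − 0.5)) = 18.
- At 85%, n = 300 × 0.85 = 255 per arm. SE = 18 × √(2/255) = 1.594; 5/1.594 − 1.96 = 1.18; power 88.0%.
- At 82%, n = 300 × 0.82 = 246 per arm. SE = 18 × √(2/246) = 1.623; 5/1.623 − 1.96 = 1.12; power 86.9%.

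The claim is confirmed in both scenarios, and nothing in this point changes it.

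**Step 2: participants without a 6-month assessment.**

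- At 85%: 600 × (1 − 0.85) = 90.
- At 82%: 600 × (1 − 0.82) = 108.

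These are participants, not missed events.

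**Step 3: share of SAE cases among those participants.** Let f be the follow-up rate and RR the event risk in those not followed up relative to those followed up. Then

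share = (1 − f) × RR / [f + (1 − f) × RR].

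The share does not depend on the unknown event rate. It does depend on RR, which is an assumption.

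| Assumed RR | f = 85% | f = 82% |
|---|---|---|
| 1 | 0.15/1.00 = 15% | 0.18/1.00 = 18% |
| 2 | 0.30/1.15 = 26% | 0.36/1.18 = 31% |
| 3 | 0.45/1.30 = 35% | 0.54/1.36 = 40% |

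The table gives the share of cases falling in the group for which no SAE-finding procedure is stated. It is the share actually missed only if nobody learns of any of them another way.

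**Step 4: could CDW supply the events?** Participants are established VA patients: "We will include Veterans who have been receiving care at the recruiting VA site for ≥ 1 year prior to recruitment". CDW is already used through the study for refill adherence and, for blood pressure, over the whole participation period. A search for deaths and VA admissions could therefore be run for all randomised participants. How complete it would be, particularly for care outside the VA, cannot be determined from the documents.

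**The case against.** The strongest case on the other side has four parts.

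- **The protocol names a time, not an interview.** In Table 8 the 6-month time point is not limited to self-report, since blood pressure there has both the cuff and CDW as sources. A record pull at month 6 would fit the protocol's wording. Only the SAP speaks of events being reported, and that document still describes in-person visits that the protocol has replaced with phone visits. This stands as far as it goes: self-report alone is not established. But no record pull for SAEs is stated either.
- **Staff may hear of events in other ways.** Possible routes are the call to drop-outs, a dashboard that shows non-response, a phone line kept open during follow-up, withdrawal by the local investigator for medical reasons, and the rule that sites communicate any SAE. These do rule out inferring that every death before month 6 is missed, or that 90 participants have no SAE ascertainment at all. None of them, however, is specified as a way of finding SAEs. The last only routes events already known.
- **CDW coverage is not shown.** A reader might infer that CDW covers everyone's events. The documents do not say that it holds all deaths or hospitalisations, and the planned whole-period pull is described for blood pressure. This stands. CDW can be searched for all participants, but its yield is unknown and the search would be an additional extraction.
- **The trial is low-risk and no between-arm safety analysis is planned.** Bias between arms needs differential loss, for which the documents give no evidence. This stands too. Low expected risk justifies an inexpensive method, but it does not explain having no stated method for those who die or are lost.

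**Conclusion.** The point holds as a gap in ascertainment. The 6-month follow-up is the only stated collection point for SAEs in both documents, and no procedure covers participants who die or are not reached. On the plan's own rates, 90 (85% follow-up) to 108 (82%) of 600 would lack a 6-month assessment. Their events may be missed or learned of only informally, and early events in any participant may be reported up to about 6 months late.

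The number of missed events cannot be computed. If the risk in those lost is one to three times that in those followed up, 15% to 40% of SAE cases would fall in the group without a stated procedure. That range rests on the assumed relative risk and on treating the power calculation's follow-up rate as the rate of 6-month contact. The documents do not support the conclusions that all deaths go unrecorded, that CDW would recover everything, or that SAE counts are biased by arm. The primary power calculation is unaffected. The change is worth making because it is cheap and also helps explain missing outcomes.

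**What to change.** In Protocol 6.0 and in the SAP under Monitoring Adverse and Serious Events, add that:

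1. deaths and VA hospitalisations from randomisation to 6 months will be searched in CDW for all randomised participants, as far as authorisation allows after withdrawal, in addition to self-report at 6 months;
2. these events will be summarised by arm, with a note that events outside the VA may be under-captured.

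In the SAP under Missing Data/Subject Dropouts, add that recorded deaths will be used to classify missing 6-month blood pressure.

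Protocol 5.7 does not address data access after withdrawal, so what is permitted there should be stated. Table 8, which lists VA utilisation at baseline only, should be updated to match. Repeating the search at intervals during the study would shorten reporting delay, but that is an optional choice about monitoring intensity.

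**Cost.** An amendment and one data extraction beyond the blood pressure and refill pulls already planned. The admissions data may also serve the SAP's budget impact analysis, which names HTN-related hospitalisations as a possible saving. Events outside the VA still depend on self-report. Sample size and power do not change.

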- Setting and Sample: 600 African-American Veterans with hypertension. Veterans will be recruited from two VA healthcare sites with known disparities in hypertension control.
- Design: Within-site randomization of Veterans
- CTC Intervention: An integrated peer narrative-based intervention (VIEW > SELECT > GET), aligned with the process of providing over-the-phone guidance to Veterans as they (a) **View** the Veteran videos; (b) **Select** a preferred video narrative; and (c) Sign up to **Get** 6-months of narrative, educational and assessment texts through the HealtheDialog Texting system. We will be guiding the Veteran in (1) at-home BP check, (2) selection of a preferred veteran storyteller after viewing all stories; (3) using this choice to inform selection of a texting protocol; (4) Receipt of 1 month of texts; and (5) follow-up assessment at the end of 6 months.
- Control: 6-month VA HTN texting protocol without narrative component
- Blood pressure will be checked with guidance from the RA over-the phone using an at home BP monitor at baseline and at a 6-month follow up for both arms.

HealtheDialog Texting system, Sending and Receiving Texts

- The Office of Connected Care (OCC), with whom we have partnered, has invested in HealtheDialog, an automated text messaging system recently developed and field-tested in five VA facilities. Text messages are automatically sent from the pre-programmed automated VA text messaging system to users. Veteran participants will receive text messages delivered using this VA HealtheDialog texting system.

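### The hypertensive-urgency referral and physician letter apply only at baseline, although the same home blood pressure reading is taken at 6 months in both arms

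*Protocol*

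**What the plan says.** Protocol section 6.0 (Reporting) sets the rule. Its timing is "At the time of baseline visit, patients experiencing hypertensive urgency". The threshold is systolic pressure of at least 180 or diastolic of at least 120, whether or not there are symptoms. The action is that such patients "will be referred to urgent care and a notification letter will be sent to their primary care physician".

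The SAP, under Monitoring Adverse and Serious Events, has the same threshold and action with different timing: "At the time of recruitment, patients experiencing hypertensive urgency". The natural reading of recruitment here is the baseline visit.

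Blood pressure is scheduled twice. Protocol section 5.1 has it checked with the research assistant (RA) on the phone, "using an at home BP monitor at baseline and at a 6-month follow up for both arms". Section 5.5 agrees: "blood pressure will be checked by participant through home BP monitor at baseline and at 6 month follow up". Table 8 lists measured BP at both time points.

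Two other provisions reach the 6-month call. Section 6.0 continues with "All AE's reported at baseline and 6-month follow-up will be recorded by the RA", for submission at Continuing Review. Section 5.2 has the RA confirm identity and location at the start of both calls: "This will provide RAs the ability to notify emergency personnel in the event that an emergency response is needed for any reason".

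**The concern.** The plan already treats a reading of this size as needing action even in someone who feels well. It gives no reason why the same value, obtained the same way, should need none six months later. An RA following the text literally has a required step at baseline and none at follow-up.

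The participant with a very high, symptom-free reading at 6 months is the one exposed. The incentive paragraph in section 5.2 counts two visits in all, so the follow-up call is the last scheduled study contact. The reading is taken at home, so the RA may be the only person other than the participant and any helper who knows of it. Eligibility (section 5.4) sets no upper limit on blood pressure, so such readings are not excluded by design.

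**Working it through.** **Comparison of the text.** The question is whether any provision attaches a clinical action to a symptom-free 6-month reading of at least 180 systolic or 120 diastolic.

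| Provision | Applies at 6 months? | Tied to a BP value? | Action |
|---|---|---|---|
| Urgency rule, protocol 6.0 | No, baseline visit only | Yes | Referral and letter |
| Urgency rule, SAP | No, recruitment only | Yes | Referral and letter |
| AE recording, protocol 6.0 | Yes | No | Recorded, sent at Continuing Review |
| SAE reporting, protocol 6.0 | Yes | No, death or hospitalization only | Reported |
| Location check, protocol 5.2 | Yes | No | Makes an emergency call possible |
| Withdrawal, protocol 5.7 | Any time | No | Participant may be withdrawn |

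No row has a BP trigger at 6 months. The omission is not just loose wording: the AE sentence that follows the urgency rule in section 6.0 names both visits, while the urgency sentence names one. Nor does AE recording fill the gap. The SAP counts urgency as an AE when symptoms are reported, and neither document defines a symptom-free high reading as an AE.

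**Plan's own figure.** The plan states over 80% power for 5 mm Hg with N = 600, 85% follow-up, correlation 0.5 and SD 18 (protocol 5.6; SAP, Power Calculations). The concern does not depend on this. It is reproduced only to confirm the N and SD used below.

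- SD of change = 18 × √(2 × (1 − 0.5)) = 18.
- Per arm: 300 × 0.85 = 255. SE = 18 × √(2/255) = 1.594. 5/1.594 − 1.96 = 1.18, so power is 88.0%.
- At 82% follow-up (246 per arm), power is 86.9%.

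Both agree with the stated figure.

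**How many participants.** Six-month readings: 600 × 0.85 = 510. Expected number with systolic at or above 180 = 510 × P(Z ≥ (180 − mean)/18). The SD is the plan's; it is not labelled systolic and is taken as such here. The mean and the normal shape are assumptions, because the documents give no mean.

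| Assumed 6-month mean | z | Tail probability | Expected of 510 | Expected of 492 (82% follow-up) |
|---|---|---|---|---|
| 125 | 3.056 | 0.00112 | 0.57 | 0.55 |
| 135 | 2.500 | 0.00621 | 3.17 | 3.06 |
| 145 | 1.944 | 0.02592 | 13.22 | 12.75 |

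A wider range is possible: 1.4 at a mean of 130, 6.7 at 140 and 24.4 at 150. The chance of at least one such reading, 1 − (1 − p)^510, is about 75% at a mean of 130, 96% at 135 and over 99% at 140 or above. Readings that cross only on the diastolic limit are not counted.

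**The case against.** The strongest reply is that the wording gap is shown but a gap in actual protection is not. Section 5.3 says RAs are trained in procedures for both the baseline and follow-up visits, and those procedures are not in the documents; a blood pressure step could sit there. That stands as a limit on what can be known. It does not rescue the protocol text, which states the rule for one visit only.

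Second, some cover exists at 6 months. The RA knows where the participant is and can call for help, and AEs are recorded and communicated under section 8.0. This covers a participant who is visibly unwell. It does not clearly cover one who is symptom-free, the case the existing rule was written to include.

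Third, these are established patients with at least one year of care at the site, two or more visits in the past year and a BP medication, so the study is not their only route to detection. That is fair, and it lowers the likely harm, but it applies equally at baseline, where the plan still requires the referral and letter.

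Fourth, the count depends mostly on the assumed mean: from 125 to 145 it changes about 23-fold (13.22/0.57). The number of home readings could also be below 510, since Table 8 allows 6-month values from VA records. Both points stand. The figures support the statement that cases are probably few, and no more.

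Finally, the SAP's Data Collection section describes RA measurement in person, not at home. That affects how the reading is taken, not the gap: both documents schedule it at baseline and 6 months.

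**Conclusion.** The concern holds. Both documents limit the urgency referral and letter to the start of the study, both schedule a second reading at 6 months, and no provision available for review attaches an action to a symptom-free reading above the threshold at that visit. The textual finding rests on no assumption beyond the natural reading of recruitment in the SAP, and the protocol text alone is enough to establish it.

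The size is small: roughly 1 to 13 participants by systolic pressure for assumed means of 125 to 145, more if the mean is higher, plus some by diastolic pressure. The point concerns participant safety only. It does not touch the primary analysis, alpha, power or sample size. It should be corrected because the correction is cheap, not because the trial's conclusions depend on it.

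**What to change.** In protocol section 6.0, have the urgency sentence name both the baseline visit and the 6-month follow-up visit, and leave the threshold and action as they are. Use the same timing in the SAP under Monitoring Adverse and Serious Events, in place of the reference to recruitment.

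The cost is one sentence in each document and, under the assumed means of 125 to 145, about 1 to 13 extra referrals and letters over the whole trial by systolic pressure, with some more by diastolic. The action would follow the 6-month outcome reading, so it cannot alter that reading, and it would apply equally in both arms. If the RA visit procedures already cover the 6-month reading, only the wording changes.
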